Breathing Techniques and Meditation for Health Care Workers During COVID-19

PI: [name] MD

Collaborators: [name], [name], [name] MD [name] MD [name] MS

Senior Authors: [name] PhD [name] MD

Introduction:

Pranayama is a term used to describe breathing techniques that are an integral part of yoga practice. Numerous studies have shown the benefit of yoga in healthy volunteers and cancer patients. (1,2, 3,4, 5, 6, 7) The benefits range from decreasing inflammation as evidenced by reduction of inflammatory cytokines to improvement in immune system as evidence by increasing non-killer/NK cells. (8) In our own studies, we have shown evidence of yoga improving chemotherapy-related cognitive dysfunction and reducing anxiety in cancer patients and caregivers in addition to improving both their quality of life. (1,9) The pandemic COVID-19 has created chaos and distress for the entire world, especially for healthcare workers. Here we suggest a series of 3-minutes breathing or pranayama practices followed by 2 minutes of meditation – overall 5 minutes to complete. The purpose of this study is to determine the effects of web-based breathing techniques and meditation on lung health and building resilience among health care workers dealing with the COVID-19 pandemic.

AIMS:

Primary Outcome:

To demonstrate the feasibility of a short pranayama or breathing techniques and meditation during Covid-19 pandemic. Feasibility will be defined as recruitment of 50 participants to the study within 2 months and acceptance of the study defined as more than 50% of participants perceive the intervention as useful.

Secondary Outcomes:

1. To determine the adherence to the practice assessed as at least 50% of participants implement the intervention for 3 or more times in a week by the end of week 1/day 7 (+ 3 days)
2. To determine the change in resilience, perceived stress and psychological impact from day 0 to day 28 as measured by the Brief Resilient Coping Scale (BRCS), Perceived Stress Scale (PSS4), and COVID-19 Stress among health care workers questionnaire
3. To determine the changes in breath holding time measured weekly for 4 weeks
4. To determine the differences in breath holding time between those who are adherent and those who are not adherent to the practice

Background/Rationale:

Current COVID-19 climate and stress on health care:

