- While performing this practice, participants will be instructed to take a 15- 20 seconds break if feeling dizzy.
- Participants will be instructed to not stress the body or overdo the exercise beyond capacity.

Step 3: Participants will be instructed to close mouth, inhale fully and simply sit for 30-60 seconds in full inspiration. After 30-60 seconds, exhale with a constriction in pit of throat and relax.

Upon completion of breathing techniques, participants will be instructed to sit in meditation for 2 minutes or longer with eyes closed. Participants will be instructed to not judge their thoughts, to be an observer, and just let their thoughts pass by without focusing on anything.

If you feel short of breath, or unable to perform the practices please do not continue with the practice. Please contact your doctor for further medical attention and notify the study team.

Video link of the practice is as follows-

<https://www.youtube.com/watch?v=IP1Y1bk1YgU>

Measures: The following measures will be completed during the course of 4 weeks through a REDCap data base

Adherence: Participants will keep a record of when they practiced each day to report in the survey how many times a day and how many days a week participant practiced for each of the 4 weeks.

Breath holding time: At baseline and the end of each week, participants will count how many seconds they can hold their breath at one time. Participants will be asked to use the stopwatch on their smartphones to time breath holding. They will first empty their lungs as much as possible with an extended exhale pulling in their diaphragm using abdominal breathing. They will then inhale fully extending their diaphragm out and start timing how many seconds they can hold their breath. After a 2-

minute rest period they will repeat and record the second number. They will record both numbers at end of each week and report the results in the survey.

Meditation perception questionnaire (including perception of usefulness): At the end of each week, participants will be asked 7 questions regarding their perception of practice such as feeling more peaceful, hopeful, relaxed, in more control of life, if they noticed improvement in their breathing, if they found the practice useful, and if they will continue to engage in the practice. We used this questionnaire in our previously published meditation study (14) and added 2 questions.

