Exploratory regression analysis for adherence to protocol for various outcomes is also planned. Protocol adherence for the study has been defined as participation in the intervention for more than 3 days in a week. Participant perception will be measured using a survey. Continuous and dichotomous data will be reported and assessed in a similar fashion as above.

Given the continuous nature of the scale, differences between scores will be assessed with a paired parametric or non-parametric t-test. In the absence of randomization, unadjusted and adjusted linear regression will be utilized in order to account for differences that persist. Our primary analyses will be assessed using intention-to-treat principles. In order to assess whether there are differences between baseline and at various intervals, we will employ the use of paired t-tests as appropriate.

For the analyses of the changes of variables over time (starting from baseline), we will also use linear mixed-effects models.

Risks:

The risk to the subject is minimal as intervention involves breathing techniques based on yoga and meditation.

Potential physical risks of the study interventions:

The interventions offered in this study are simple and only involves meditation and breathing practices. Participants may feel light headed for a short period of time. As such, there are no physical risks expected with these interventions. Similarly, by assessing stress or well-being measures, we do not anticipate any risk of physical harm to any of the research subjects. Hand held spirometer is easy to use. The twenty participants selected for this extra measure will be nurses, physicians or respiratory therapists who report knowing how to use the spirometer.

Potential psychological risks:

It is possible that there could be psychological or emotional risk to subjects in this study if they were to become aware of their performance in assessments and more so than they would be if they were not participating in the study. Subjects will not be given the scores of their assessments, but if they were to become aware of a decline in their performance this could be stressful or disconcerting to the subject. For additional counseling regarding any psychological or emotional distress stemming from this, participants will be referred to Employee Assistance Program (EAP) at the request of the subject.

Data security and privacy:

Risk of breach of confidentiality:

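### The plan anticipates light-headedness and dizziness, but no described measure asks every participant about symptoms and no harm summary is planned, so acceptance can be reported without a symptom rate

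*Combined protocol and SAP*

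**What the plan says.** All references are to the Combined protocol and SAP.

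- **Effects anticipated.** Risks (physical risks): "Participants may feel light headed for a short period of time. As such, there are no physical risks expected with these interventions". Intervention, notes after Step 2: "participants will be instructed to take a 15- 20 seconds break if feeling dizzy". Intervention, closing instruction: "If you feel short of breath, or unable to perform the practices please do not continue with the practice". The closing instruction goes on to tell the participant to contact a doctor and inform the study team.
- **Weekly perception questionnaire** (Measures): seven questions are announced for the close of every week. The first six topics listed are "feeling more peaceful, hopeful, relaxed, in more control of life, if they noticed improvement in their breathing, if they found the practice useful". The seventh, which ends the list, concerns intention: "and if they will continue to engage in the practice".
- **Other weekly content** (Measures): a practice record, "to report in the survey how many times a day and how many days a week participant practiced for each of the 4 weeks", and two breath holding times.
- **Global Symptom Evaluation (GSE), part 2** (Measures): given once, at week 4 or on removal, with answers yes, no or uncertain. It covers whether taking part was worthwhile, whether they would do so again, whether they would refer others, and whether quality of life was affected for better or worse. Its stated purpose is to show burden or benefit.
- **Acceptance** (Primary Outcome, repeated in Data Analysis): "acceptance of the study defined as more than 50% of participants perceive the intervention as useful".
- **Data Analysis** contains no adverse-event or tolerability summary and does not link the GSE to acceptance.

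**The concern.** A feasibility pilot is where one would expect to learn how well an unsupervised, video-guided practice is tolerated. Here the plan itself foresees light-headedness and dizziness, yet whether either is recorded depends on a participant volunteering it. Dizziness carries an instruction to pause but none to report. A negative answer on usefulness cannot separate a practice that did nothing from one that made the participant dizzy. At stake is what can be said about tolerability beside the acceptance result: volunteered reports have no usable denominator, because silence may mean either no symptom or an unreported one.

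**Working it through.** **1. Is a symptom item hidden in the weekly questionnaire?** The text announces seven questions. The topics named are peaceful, hopeful, relaxed, control of life, improved breathing, usefulness and intention to continue. That is 5 on improvement + 1 on usefulness + 1 on continuing = 7. The list matches the announced count, so the words introducing it as examples leave no room for an eighth, symptom item.

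**2. Is one found elsewhere?**

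| Measure | When | Asks everyone about a physical symptom of practice? |
|---|---|---|
| Practice record | weekly | No; counts only |
| Breath holding | baseline, weekly | No; times only |
| Perception questions | weekly | No |
| GSE part 2 | week 4 or removal | No, as described; one global quality-of-life question |
| Perceived Stress Scale (PSS-4), Brief Resilient Coping Scale (BRCS), COVID-19 stress | baseline, end | No; stress, coping and pandemic impact |
| Notice to the team | if short of breath or unable to practise | No; participant-initiated |

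The GSE is said to have five questions, and four topics are named. Its items are not reproduced, so the entry rests on the description.

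**3. The plan's own precision figure.** Sample Size Justification gives a 95% half-width of 0.098 for the usefulness proportion at N = 100 and p = 0.500. Check: 1.96 × √(0.5 × 0.5 / 100) = 0.0980. It reproduces. A symptom item changes neither this nor the power statements.

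**4. What asking everyone would give.** With no reports among n people asked, the exact (Clopper-Pearson) two-sided 95% upper limit is 1 − 0.025^(1/n).

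- n = 100: 1 − 0.025^(1/100) = 0.0362, or 3.6%.
- n = 90 (the plan's 10% attrition case): 1 − 0.025^(1/90) = 0.0402, or 4.0%.
- For comparison, 10 of 100 gives 4.9% to 17.6%.

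**5. What volunteered reports give.** The documents state neither a symptom rate p nor a reporting fraction r, so both are assumptions here. The chance of at least one report among 100 is 1 − (1 − p × r)^100.

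| Assumed p | everyone asked (r = 1) | r = 0.10 | r = 0.50 |
|---|---|---|---|
| 5% | 99.4% | 39.4% | 92.0% |
| 10% | above 99.9% | 63.4% | 99.4% |

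At p = 10%, 10 affected people are expected, but only 10 × 0.10 = 1 to 10 × 0.50 = 5 reports. The larger difficulty is that the reported fraction estimates p × r with r unknown. Two reports from 100 would fit a rate of 0.02 / 0.50 = 4% or of 0.02 / 0.10 = 20%.

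**The case against.** A reader might infer that harms go uncollected. The documents do not support that: people who are short of breath or unable to practise are told to notify the team, and the GSE can register a negative effect on quality of life, including at removal. Both routes are weak, but they exist.

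Other strong readings also fail:

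- **The weekly survey asks only about benefits.** The continuation question is neutral, adherence and breath holding are recorded, and any perception question can be answered in the negative. Poor tolerability can therefore lower the acceptance result, though without showing why.
- **Three expected effects are named.** Only light-headedness is stated as a possible effect. Dizziness and shortness of breath appear in conditional instructions, and shortness of breath is not attributed to the practice.
- **Someone who stops because of dizziness shows up only as non-adherent.** If unable to practise, that person is asked to notify the team; if removed, they complete the GSE.
- **Secondary Outcome 4 is distorted.** Nothing in the documents gives a direction or size for such an effect. Reasons for stopping would help interpret the adherent versus non-adherent comparison, but its definition would stand.

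It can also be said that perceived usefulness is a legitimate acceptance criterion in a study the plan calls minimal risk, and that the Risks sentence is awkward drafting that affects no analysis. Both points are fair. Consent pages are not part of the text reviewed, and a separate adverse-event procedure cannot be ruled out. What remains is that no described measure asks everyone, and no summary is planned.

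**Conclusion.** The point holds as a gap in systematic collection and reporting, not as an absence of any route for harms and not as a flaw in the acceptance criterion itself. Followed as written, the pilot can meet its usefulness threshold and still be unable to state what proportion of participants had the light-headedness or dizziness it foresaw. The numerical loss is the bound in step 4 of the working, which is available only if all participants are asked and answer. The conclusion rests on the measures as described; the rates in step 5 are illustrative and it does not depend on them. Sample size, power and the stated precision are unaffected. This is a worthwhile, inexpensive improvement.

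**What to change.** 1. Add a short item to each existing weekly REDCap survey and to the form completed at removal. It should ask whether light-headedness or dizziness, shortness of breath, another symptom or none occurred during or after practice, and whether practice was stopped or skipped because of it.
2. In Data Analysis, plan to report the number and percentage of participants with each answer, with exact two-sided 95% confidence intervals and the number who answered, beside the usefulness result. The acceptance definition need not change.
3. Use the recorded reasons for stopping when interpreting Secondary Outcome 4, leaving the comparison as defined.
4. Reconcile the Risks conclusion about physical risk with the light-headedness stated just before it and with the dizziness and shortness-of-breath instructions under Intervention.

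The cost is an amendment, a few extra answers in each of four weekly surveys and at removal, and one descriptive table. Prompting will also bring in some trivial symptoms, which should be borne in mind when reading the percentages.

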Global Symptom Evaluation (GSE): The GSE has 2 parts and participants will only complete part 2. (15) Part 2 consists of 5 questions that evaluate whether participating in the study was worthwhile, whether they would participate in the study if they had to do over again, whether they would refer the study to others, and whether it had a positive or negative impact on quality of life. The answers consist of yes, no, and uncertain. We will only use the second part of GSE (Modified GSE Questionnaire) and it will only be asked at the end of the study. These questions will help determine if participating in the study was burdensome or beneficial to the participants. Participants will complete the questionnaire at the end of the study at week 4, or at the time of removal from the study.

Perceived Stress Scale 4 (PSS-4): The PSS will be asked at baseline and the end of the study. (16) The questions in this scale ask about participants feelings and thoughts during THE LAST MONTH. In each case, please indicate your response by placing an "X" over the square representing HOW OFTEN you felt or thought a certain way.

1. In the last month, how often have you felt that you were unable to control the important things in your life?
2. In the last month, how often have you felt confident about your ability to handle your personal problems?
3. In the last month, how often have you felt that things were going your way?
4. In the last month, how often have you felt difficulties were piling up so high that you could not overcome them?

The responses include: Never, Almost Never, Sometimes, Fairly Often, Very Often.

(0 1 2 3 4)

Lowest score: 0, Highest score: 16. Higher scores are correlated to more stress

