Stress among healthcare workers: This measure will be asked at baseline and the end of the study. Drawing from published measures that have assessed the impact of pandemics (H1N1) (17) and other major national stressors such as 9/11, a 29-item measure was developed to assess COVID-19 specific psychological distress (e.g., fear, anxiety and depressive symptoms), and financial and social disruptions. Items also assess resiliency factors such as social support, perceived benefits under times of stress, and ability to manage stress. Responses are provided in a Likert like scale (from 1 to 4) where participants are asked to rank statements from "strongly disagree" to "strongly agree." The measure provides a total score summary that indicates the degree to which the COVID-19 pandemic has negatively impacted the participant. Items that tap into resiliency are reverse scored. In addition to the summary score, based on psychometric analyses upon collection of the data, the scale is expected to yield 5 subscale scores: COVID-19 Specific Distress; Disruption to Daily Activities and Social Interactions; Financial Hardship; Perceived Benefits; and Perceived Stress Management Skills. These answers may not change over time, and may even worsen with time depending on the pandemic effect such as number of cases and burden on health care organization.

Brief Resilient Coping Scale-BRCS: The BRCS will be asked at baseline and the end of the study. The BRCS has four items. (18) The participants are asked to select one option for each statement to indicate their level of disagreement or agreement with each item on a 5-point Likert-type scale, ranging from 1 = *strongly disagree* to 5 = *strongly agree*

1. I look for creative ways to alter difficult situations
2. Regardless of what happens to me, I believe I can control my reaction to it
3. I believe that I can grow in positive ways by dealing with difficult situations
4. I actively look for ways to replace the losses I encounter in life

Demographic information includes age, gender, race, ethnicity, occupation, marital status, COVID status, directly managing patients with COVID (Yes/No), work location, and h/o respiratory disorder (type, medications on daily basis or as needed). At the end of study, we will also ask the participants if they tested positive for COVID during the study time.

Statistical Considerations:

Sample Size Justification:

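### Does the missing reverse-scoring rule for PSS-4 items 2 and 3 leave the perceived-stress score undefined?

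*Combined protocol and SAP*

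**What the plan says.** Secondary Outcome 2 in the Aims is "To determine the change in resilience, perceived stress and psychological impact from day 0 to day 28". The PSS-4 is its perceived-stress instrument, given at baseline and at the end of the study.

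The PSS-4 entry under Measures cites a source for the scale and prints the four items. Item 1 asks "how often have you felt that you were unable to control the important things in your life", and item 4 asks about being overwhelmed by difficulties. Item 2 reads "In the last month, how often have you felt confident about your ability to handle your personal problems" and item 3 reads "In the last month, how often have you felt that things were going your way". One list of answers follows: "The responses include: Never, Almost Never, Sometimes, Fairly Often, Very Often". Below it is a single row of codes from 0 to 4, and then the range and direction: "Lowest score: 0, Highest score: 16. Higher scores are correlated to more stress".

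Neither this entry nor Data Analysis gives a scoring formula. Data Analysis says "Given the continuous nature of the scale, differences between scores will be assessed with a paired parametric or non-parametric t-test", without naming the instrument it refers to. For a different measure, the 29-item COVID-19 stress questionnaire, the plan does state a rule: "Items that tap into resiliency are reverse scored".

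**The concern.** A more frequent answer means more stress on items 1 and 4, and less stress on items 2 and 3. If the single row of codes is read as the scoring rule for every item, a participant who very often feels confident gains 4 points on a scale said to rise with stress. The two pairs of items would then pull against each other. A real fall in stress between day 0 and day 28 could appear as little or no change, or as a change in the wrong direction. A range check would not catch the error, because both scorings run from 0 to 16. The silence is also more noticeable because the plan states the reversal for its other mixed-direction measure.

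**Working it through.** **Inputs.** The four items, the codes 0 to 4, the 0–16 range and the direction all come from the PSS-4 entry under Measures. Write the coded answers as x1 to x4.

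- Raw sum: R = x1 + x2 + x3 + x4.
- Items 2 and 3 reversed: V = x1 + (4 − x2) + (4 − x3) + x4.

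**The plan's range.** R runs from 0 at (0,0,0,0) to 16 at (4,4,4,4). V runs from 0 at (0,4,4,0) to 16 at (4,0,0,4). The printed range holds under both, so it cannot tell them apart.

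**The plan's direction.**

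| Answers | R | V |
|---|---|---|
| (4,0,0,4), most stressed | 8 | 16 |
| (2,2,2,2), middle | 8 | 8 |
| (0,4,4,0), least stressed | 8 | 0 |

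Only V puts the stress extremes at the ends of the printed range. Under R, the top score requires a participant who is very often confident and also very often unable to cope.

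**Is the scoring unique?** Each of the four items is either reversed or not, which gives 2^4 = 16 possible rules. For (4,0,0,4) to total 16, every item must contribute its maximum of 4. Items 1 and 4 do so only if left as coded, and items 2 and 3 only if reversed. One rule of the 16 qualifies, and it also returns 0 for (0,4,4,0).

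**How far apart are the two scores?** V − R = 8 − 2(x2 + x3). This is zero only when x2 + x3 = 4, which covers 5 of the 25 pairs. The totals therefore differ in 20/25 × 625 = 500 of 625 patterns (80%), by at most 8 points. This counts patterns, not participants.

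**Effect on change, if a raw sum were used.** Suppose items 1 and 4 each improve by a points, and items 2 and 3 each improve by b. The change in R is −2a + 2b = −2(a − b). The change in V is −2a − 2b = −2(a + b). The raw sum shows the fraction (a − b)/(a + b) of the change in V:

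| b/a | Fraction shown |
|---|---|
| 0 | 100% |
| 0.5 | 0.5/1.5 = 33% |
| 0.75 | 0.25/1.75 = 14% |
| 1 | 0% |
| 1.33 | −0.33/2.33 = −14% |
| 2 | −1/3 = −33% |

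For example, a one-step improvement on every item, from (3,1,1,3) to (2,2,2,2), moves V from 12 to 8 and leaves R at 8. The harm from a raw sum would be real. The open question is whether the plan leads anyone to compute one.

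**What depends on the score.** The primary outcome is recruitment plus perceived usefulness, and it does not use the PSS-4. The calculations in Sample Size Justification are in standard-deviation units for a generic paired comparison. They check independently of any scoring rule: power is 0.8002 at n = 100 with 0.283 SD, and 0.8012 at n = 90 with 0.299 SD, against the stated 80%.

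**The case for a change.** The strongest case for a change is that a protocol which prints its own items, codes, range and direction should not leave the one connecting rule to inference. The plan cites a source for the scale but does not say that scoring follows it. It states reversal for the COVID-19 stress measure, so its authors evidently regard such a rule as worth writing down. Someone building the score from the printed codes alone could get it wrong, and the range would give no warning. One sentence would remove the doubt.

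The facts in this stand: the rule is unwritten, the range check is blind to the error, and a raw sum would be badly attenuated. The claim of a contradiction does not stand. The row of codes belongs to the answer options, in a paragraph that tells the respondent how to mark an answer. It is not an instruction to add raw codes. The conflict appears only if the reader supplies that step and then ignores the direction printed straight after it. The reversal stated for the other measure cuts both ways: it makes the silence more visible, but it also shows a team that knows mixed-direction items must be aligned.

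**Conclusion.** No change to the plan follows. The missing sentence is a gap that the plan's own text fills: the stated direction and range, read with the item wording, lead to a single scoring rule, with items 2 and 3 reversed. This conclusion does not rely on the cited source for the scale, which is not available here.

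The possible damage is large only if the four raw codes are summed. In that case both extremes score 8, and the observed change is (a − b)/(a + b) of the true one. The documents neither order that sum nor show that it was used. Putting a figure on lost power would mean assuming how strongly each item reflects stress, the retest correlation and the size of the effect, none of which the plan gives, so no such figure is offered.

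The reach is also narrow: one of three instruments in one of four secondary outcomes of a feasibility study without randomization. The plan has survey data entered directly into REDCap. If the item answers are kept there, which is an assumption, a mis-scored total could be recomputed without new data. Writing the rule down would be harmless, but it would only record what the stated direction already requires.

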This study is being conducted with HCWs who are currently at the forefront of pandemic management. Due to overwhelming response and willingness to participate in the study, we decide to increase our accrual from 50 to 100. The increased sample size will allow for increased precision or power in assessing both the primary and secondary objectives. When the sample size is 100, a two-sided 95% confidence interval (CI) for the proportion of perception of the intervention as usual using the large sample normal approximation will extend 0.098 from the observed proportion for an expected proportion of 0.500. In addition, a sample size of 100 will have 80% power to detect a difference in mean of 0.283 standard deviation (SD) unit between baseline and a time point after baseline, using a paired t-test with a 0.050 two-sided significance level. Attrition is unlikely in our study setting given that the participants are HCWs during the pandemic of COVID-19. However, in the unlikely case of a 10% attrition, a resulting sample size of 90 ($=100*0.9$) will have 80% power to detect a difference in mean of 0.299 SD unit between baseline and a time point after baseline, using a paired t-test with a 0.050 two-sided significance level. In both scenarios, the detectable effect size is considered medium.

Data Analysis:

Baseline characteristics of participants will be recorded. Continuous data will be presented as means \pm standard deviation or median (interquartile range) depending on the distribution of the data and assessed with a parametric paired t-test or non-parametric Wilcoxon signed rank test for the changes between time points, as appropriate. Normality will be assessed with the Shapiro-Wilk test. Categorical data will be presented as frequencies and percentages and assessed with a chi-square or Fisher's exact test, as appropriate. SPSS will be used for all analyses with two-sided p-values < 0.05 considered statistically significant.

Feasibility will be defined as recruitment of 50 participants to the study within 2 months and acceptance of the study defined as more than 50% of participants perceive the intervention as useful. Adherence will be assessed using data from how often participants complete their breathing techniques. This will be reported as the percentages of completed activities out of the total required per protocol.

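### A normality pre-test chooses which effect is reported; on PSS-4 and BRCS it can reject through coarseness alone and leave a median change of 0, so the mean change should be fixed in advance

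*Combined protocol and SAP*

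**What the plan says.** Under Statistical Considerations, Data Analysis, the plan presents continuous data as mean with SD or as median with interquartile range, "depending on the distribution of the data and assessed with a parametric paired t-test or non-parametric Wilcoxon signed rank test". The one criterion offered is "Normality will be assessed with the Shapiro-Wilk test". No significance threshold is given for that test, and the plan does not say whether it is run on the scores at each visit or on the changes. Later in the same section the scale scores are called continuous, and the parametric or non-parametric choice is repeated. Linear regression and linear mixed-effects models for change from baseline are planned as well, with no order of precedence.

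The Sample Size Justification is written for a mean: 100 participants give "80% power to detect a difference in mean of 0.283 standard deviation (SD) unit", "using a paired t-test with a 0.050 two-sided significance level".

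The Measures section defines PSS-4 as "Lowest score: 0, Highest score: 16". BRCS has four items scored 1 to 5, so its total runs from 4 to 20. The COVID-19 stress questionnaire has 29 items scored 1 to 4, so its total runs from 29 to 116. The change in all three from day 0 to day 28 is secondary outcome 2.

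**The concern.** A change score on PSS-4 or BRCS is a whole number, often of only a few points. Shapiro-Wilk compares the ordered data with normal quantiles, so heavy ties count against normality even when the underlying change is normal. With 90 to 100 pairs it has the power to notice them. The outcome then moves to the median and the Wilcoxon test for a reason unrelated to skewness, outliers or the intervention.

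On a coarse scale the median change can be exactly 0 while the mean has moved by the amount the study was sized for. A reader could meet a median change of 0 beside a significant Wilcoxon test. The short scales could be summarised by medians and the 29-item total by a mean, although all three belong to one objective. A mixed-model mean change could appear next to a median of 0, with nothing in the plan to say which is the result.

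**Working it through.** **Inputs.** From the documents: two-sided 0.05, 80% power, 0.283 SD at n = 100, 0.299 SD at n = 90, and the score ranges. Assumed: the SD of change, which the documents do not give and which is therefore varied; a normal underlying change; and Shapiro-Wilk applied to changes at 0.05.

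**1. The plan's own figures.** Power of a paired t-test is P(T > t(0.975; n−1)), where T is noncentral t with noncentrality d√n.
- n = 100: 0.283 × 10 = 2.83 on 99 df, power 0.800. The detectable effect is 0.2829.
- n = 90: 0.299 × 9.487 = 2.84 on 89 df, power 0.801. The detectable effect is 0.2985.

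Both reproduce.

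**2. Pre-test and median together.** Normal changes with mean 0.283 × SD were rounded to integers (n = 100, 4,000 runs per row):

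| SD of change | True mean change | Shapiro-Wilk rejects | Median exactly 0 | Both |
|---|---|---|---|---|
| 1.5 | 0.42 | 100% | 61% | 61% |
| 2 | 0.57 | 91% | 35% | 33% |
| 2.5 | 0.71 | 50% | 22% | 12% |
| 3 | 0.85 | 26% | 15% | 5% |
| 4 | 1.13 | 12% | 9% | 2% |
| 10 | 2.83 | 6% | 2% | <0.1% |

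The same data before rounding are rejected in 4% to 6% of runs, so the excess comes from coarseness.

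Simulating the two scores instead (rounded and clipped to 0–16, correlation 0.5) gives 100%, 90%, 48% and 26% rejection at score SD 1.5, 2, 2.5 and 3, and 62%, 32%, 11% and 5% for both events. With r = 0.5 the SD of change is SD × √(2(1 − 0.5)) = SD, so the two sets are comparable.

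**3. Hand check of the median column.** With 100 pairs the median is 0 essentially when at least 51 rounded changes are 0 or below. The chance for one person is p = Φ((0.5 − 0.283 × SD)/SD).
- SD 2: p = Φ(−0.033) = 0.487. The count has mean 48.7 and SD √(100 × 0.487 × 0.513) = 5.0, so P = 1 − Φ((50.5 − 48.7)/5.0) = 1 − Φ(0.36) = 36%.
- SD 3: p = Φ(−0.116) = 0.454, so P = 1 − Φ((50.5 − 45.4)/4.98) = 1 − Φ(1.02) = 15%.

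Both agree with the table.

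**4. Sensitivity.**
- n = 90 with 0.299 SD: rejection 82% at SD 2 and 41% at SD 2.5; both events 26% and 9%.
- Four five-category items simulated directly, symmetric or skewed, SD of change 2.1 to 3.3: changes rejected in 19% to 89% of runs; both events in 3% to 30%.
- If the raw scores at each visit are tested instead, at least one visit is rejected in 40% to 100% of the item-level runs.

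**5. Inference on these scales.** In the 0–16 score simulation the t-test is significant in 78% to 79% of trials and Wilcoxon in 77% to 78%. Type I error is 4.8% to 5.6% for the t-test, the Wilcoxon test and the pre-tested choice alike. At SD 2, 17% of the rounded-change runs combine rejection, a zero median and a significant Wilcoxon test.

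**The case against.** The strongest reply is that little is lost. Wilcoxon performs almost as well as the t-test here. The planned regression and mixed models estimate a mean change whatever the pre-test says. The scales are secondary outcomes of a feasibility study, and no decision rule uses their effect sizes. The plan also does not say in terms that a median change, as distinct from medians at each visit, would be presented. All of this stands and limits the point to the choice of reported effect. It does not remove it, because the plan nowhere states which of the mean-based and pre-tested results is the reported one.

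Several stronger readings are tempting and not supported:

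- **That Shapiro-Wilk will reject these scales.** This depends on an SD the documents omit. Rejection is near certain up to an SD of change of about 2, about even at 2.5, and a minority outcome from 3 upward. On a 0 to 16 scale, a score SD of 1.5 puts about 95% of people within 4 × 1.5 = 6 points, and an SD of 3 spreads them over 12, so the larger values cannot be ruled out.
- **That the chance of a zero median measures the harm.** A median is reported only when the pre-test rejects, so the joint figure applies: at SD 3, 5% rather than 15%.
- **That the COVID-19 stress total suffers the same way.** With a range of 29 to 116 it is not a short scale; rejection through rounding falls to 6% at an SD of change of 10.
- **That dropping the pre-test is free for every outcome.** Breath holding is self-timed in seconds and may have heavy-tailed changes. Under assumed shapes (t with 3 df, Laplace, 5% outliers at four times the SD) with a 0.283 SD shift, the t-test has about 79% to 85% power against 90% to 97% for the pre-tested choice.

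**Conclusion.** The point holds in a limited form. A pre-test on the same data selects the reported effect, although the design is powered only for a mean change. On PSS-4 and BRCS that selection can be driven by coarseness and end in a zero median: about 62%, 32%, 11% and 5% of trials at an assumed SD of 1.5, 2, 2.5 and 3. These figures rest on a normal underlying change, a true shift equal to the powered effect, and the pre-test being applied to changes at 0.05. A reader might infer that the p-values are invalid or that power is lost on these scales; the calculations show neither. What is affected is the size, meaning and comparability of the reported effects within secondary outcome 2. The feasibility outcome and the stated power figures are unchanged. This is a worthwhile, inexpensive improvement, not a flaw that threatens the study.

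**What to change.** - **PSS-4 and BRCS, and the COVID-19 stress total for a common footing:** remove the normality pre-test. Prespecify the mean change from day 0 to day 28 with its 95% CI as the reported effect. Name one source for it, either the paired t-test or the mixed model already planned, and say that it takes precedence. Give the Wilcoxon test in every case as a sensitivity analysis.
- **Breath holding:** likewise fix the primary summary in advance, and always show both the mean-based and the rank-based analysis.

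The cost is a few sentences in the Data Analysis section, with no change to sample size or data collection. The one downside is for breath holding: if changes are heavy-tailed and the t-test is made primary, it could lose about 10 points of power or slightly more against the pre-tested choice. Showing both analyses makes that visible.
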